The following schematics outline the study design and the stimulation strategy. We will recruit 40 participants and may screen up to 60 people to achieve target subject population. Subject involvement will last approximately 2 months, including a stimulation session block - 2 daily 20 minute sessions over 5 consecutive days - and assessment sessions.

Participants will be pseudo-randomized into an active stimulation or sham stimulation arm, matched for cognitive impairment at baseline. Both acute and maintenance effects are evaluated through clinical and cognitive assessment and neuroimaging sessions at 4 time points baseline, after the first stimulation session, after 1 week and follow-up at 2 months.

Sub Study:

This is an interventional study assessing efficacy and neurophysiological correlates of tDCS in schizophrenia patients in a within subject design. The duration of the study will be in line with the 2 years of the main study. We will recruit a maximum of 20 participants. The participants will be recruited from the sham condition of the main study. After the two month follow-up (in the main study), the participants, who were randomized into the sham condition, will be asked to participate. Participation will be optional. Subject involvement will last an additional 2 months.

Study Population

We will recruit 40 subjects with a diagnosis of schizophrenia, schizopreniform disorder or schizoaffective disorder and taking antipsychotic medication. Medication history will be fully assessed with antipsychotic exposure converted into standardized equivalents.

Inclusion Criteria: a) ages 18-50 years; b) on stable doses of antipsychotic medication for at least one month; c) not taking benzodiazepines or mood stabilizers; d) Mild to severe cognitive impairment in MATRICS Consensus Cognitive Battery (composite scores < 40). Exclusion Criteria: a) DSM-5 mental retardation; b) significant head injury; c) medical illness affecting brain function or structure; d) pregnancy or postpartum (<6 weeks after delivery or miscarriage); e) significant neurologic disorder (e.g seizure disorder); f) inability to provide informed consent; g) significant color blindness that affects task performance; h) comorbidity for DSM-5 psychoactive substance use disorder within the past one month; i) positive urine drug screen (excluding THC at baseline); j) temporal relation between illness onset and head injury; and k) Taking benzodiazepines or mood stabilizers (lithium allowed).

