Sub Study:

We will only recruit from the 20 participants who were randomized into the sham condition of the main study. Inclusion: Completion of the sham condition of the main study. Exclusion: Participation in the active stimulation condition of the main study. Additionally, if the participant has 1) become pregnant, 2) stopped their antipsychotic medication 3) began taking benzodiazepines or mood stabilizers (lithium allowed), or 4) met criteria for DSM-5 psychoactive substance use disorder within the past one month, they will no longer be eligible for the sub-study.

Subject recruitment

Subjects will be recruited from the outpatient clinical programs at Baylor College of Medicine and other community psychiatric programs. These will include Ben Taub's psychiatric emergency room and inpatient and outpatient center and MHMRA. Primary clinicians at BCM will be notified of our research study. Potential subjects with a diagnosis of schizophrenia will be identified and initially approached through their primary clinician, who will ask patient's permission to be contacted by the research team. Upon obtaining patient's written permission, a staff member from the research team will contact the subject. We will also recruit participants through flyers in the community and social media, such as facebook and BCM's clinical trials website.

The screening and recruitment procedure is listed below:

Screening:

- Eligibility checklist
- Ishihara Color Blindness Test
- Urine Pregnancy test for females
- Urine drug screen, if not available from inpatient/outpatient testing

Sub Study:

- Eligibility Checklist
- Urine pregnancy test for females
- Urine drug screen, if not available from recent inpatient/outpatient testing

Screening before experimental procedures:

- EEG and MRI screening protocol prior to participating in imaging studies

Symptoms and Neuropsychological assessment: Interviews and Ratings

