Participants will be interviewed in a dedicated room at the Greenpark One building. One of the following two cognitive batteries may be administered. The BACS battery, a newly developed instrument that assesses cognitive impairments in schizophrenia takes approximately 35 minutes to complete. The constructs that are measured include verbal memory, working memory, motor speed, verbal fluency and executive functioning. The other cognitive assessment tool that could be used is the MATRICS assessment. The full MATRICS battery targets the six cognitive domains (speed of processing; attention/vigilance; working, visual and verbal memory; reasoning and social cognition) identified as being disturbed in schizophrenia. The MATRICS battery takes approximately 1 hour.

Sub Study:

MATRICS will be completed at the 1 week time point.

Safety and tolerability assessment

Clinical and neuropsychological assessments are all performed by trained research personnel to reduce the risk of distress from psychiatric interviews and experimental procedures.

Clinical Assessments

In addition to detailed demographic information (including medication and treatment information), we obtain diagnostic information using the Structured Clinical Interview for DSM-5 Disorders (SCID-5) and/or the MINI International Neuropsychiatric Interview for Psychotic Disorders Studies (MINI 7.0.2) at the discretion of the PI. Psychopathological ratings are conducted include: the Brief Psychiatric Rating Scale (BPRS), the Scale for the Assessment of Positive Symptoms (SAPS), the Scale for the Assessment of Negative Symptoms (SANS), the

Hamilton Depression Rating Scale (HDRS), the Bech-Rafaelsen Manic Rating Scale, the 7-point Clinical Global Impression (CGI) Scale, the Global Assessment Functioning (GAF), Auditory Hallucinations Rating Scale (AHRs), and Specific Level of Functioning Scale (SLOF).

Sub Study:

Psychopathological ratings listed above will be completed at the 1 week time point and 2 month time point.

Medical assessments

A medical history will be obtained on all participants.

Experimental Procedures: tDCS, EEG, MRI

tDCS

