Any unanticipated problems will be reported to IRB immediately (within 24 hours). The research team will meet on a weekly basis to review study safety issues, adverse events, data integrity and any other relevant study issues. Any significant concerns or issues during the conduct of the study will be immediately communicated to the study PI.

Data Analysis

Ratings, behavioral and neurophysiological variables will enter GLM to assess interactions of group (treatment vs sham) and time points, with planned contrasts to index size effects and trajectories. On the basis of the reported studies, our experience with the population, relatively short study duration and good overlap of the two arms conditions, we expect only minimal occurrence of data missing at random. EEG analysis will be conducted with in house MATLAB scripts and will mainly focused on time-frequency analysis for modulation of power by experimental factors (CC and WM load) and to extract phase information in order to perform phase-amplitude cross-frequency coupling analysis. Beamforming source localization will be using Fieldtrip (Nijmegen, NL). fMRI analysis will be conducted in the FSL framework (FSL, Oxford, UK). MRS analysis will be performed using the jMRUI software package version 2.2 (<http://www.mrui.uab.es/mrui>).

Regulatory Ethics Compliance

Investigator Responsibilities

The investigator is responsible for ensuring the study is performed in accordance with the protocol, current ICH guidelines on Good Clinical Practice, and applicable regulatory requirements. During the study the investigator will send the following documents and updates to the Baylor College of Medicine Institutional Review Board for their review and approval, where appropriate:

- a) Protocol amendments (excluding the ones that are purely administrative, with no consequences for subjects, data or study contact)
- b) Revision(s) to ICF and any other written materials to be provided to subjects.
- c) Revisions to compensation for study-related injuries or payment to subjects for participation in the study, if applicable.
- d) Reports of adverse events that are serious, unlisted/unexpected, and associated with the study protocol.
- e) Deviations from or changes to the protocol to eliminate immediate hazards to the subjects.
- f) Any other requirements of the IRB.

At the end of the study, the investigator will notify the IRB about the study completion.

Informed Consent

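### The group-by-time GLM states no baseline covariate, which can cost precision at 1 week, and Aim 1's two tasks have no primary measure or rule for success

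*Combined protocol and SAP*

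**What the plan says.** The confirmatory analysis is one sentence in Data Analysis: "Ratings, behavioral and neurophysiological variables will enter GLM to assess interactions of group (treatment vs sham) and time points". The only further detail on testing is that this is done "with planned contrasts to index size effects and trajectories". The contrasts are not listed, and no covariate, primary test, significance level or multiplicity rule is given there or elsewhere. On missing data the section says only "we expect only minimal occurrence of data missing at random".

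Study Design gives the visits as "4 time points baseline, after the first stimulation session, after 1 week and follow-up at 2 months". It also says "Participants will be pseudo-randomized into an active stimulation or sham stimulation arm, matched for cognitive impairment at baseline", without naming the score used for matching. Study Population sets an entry limit on the MATRICS composite, but the neuropsychological assessment section says "One of the following two cognitive batteries may be administered", the two being BACS and MATRICS.

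Objectives, Aim 1, concerns both cognitive control and working memory tasks, and Hypothesis 1 expects better performance on active stimulation. Cognitive testing and EEG lists reaction time, response and accuracy without ranking them. That section gives the visits partial roles: 1 week against baseline for the acute effect, 2 months for persistence, and the visit after the first session for exploring early predictors.

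The target is 40 participants. The Sub Study text under Study Population gives the arm size: "We will only recruit from the 20 participants who were randomized into the sham condition of the main study".

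**The concern.** Two gaps meet in one sentence of the plan.

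**Precision.** If baseline is a level of the time factor, the 1-week comparison with baseline is a difference in change scores. That gives baseline full weight even when it predicts follow-up only moderately, and so adds noise. With 20 per arm, precision is scarce, and the baseline scores are already being collected.

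**Error control.** Nothing says which task, measure or contrast decides Aim 1, or whether one task is enough. Publication Plan foresees conference presentations in the first and second year. A test chosen after arm-level results are known would carry little weight.

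**Working it through.** **Inputs.** From the documents: 40 participants, 20 per arm, four visits including baseline, two tasks. The documents give no significance level, power, SD, effect size or correlation, so there is no plan figure to reproduce. Assumed: two-sided 5%, 80% power, baseline SD of 1, baseline-to-follow-up correlation ρ from 0.3 to 0.9.

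**Step 1: precision of the 1-week contrast, equal SDs.** Variance per participant:
- change contrast: 2(1−ρ)
- baseline-adjusted: (1−ρ²) × 37/36. The factor is 1 + 1/(2×20−4) = 1 + 1/36, the expected cost of chance baseline imbalance.
- ratio: (1+ρ)/2 × 37/36

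At ρ = 0.6 the variances are 0.800 and 0.64 × 37/36 = 0.658, ratio 0.822, a saving of 18%. Detectable effects use the noncentral t distribution (adjusted 37 df; change 38 df, or 114 df if the error term is pooled over visits).

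| ρ | Ratio | Variance saved | Detectable, change (38 / 114 df) | Detectable, adjusted |
|---|---|---|---|---|
| 0.3 | 0.668 | 33% | 1.08 / 1.06 SD | 0.88 SD |
| 0.5 | 0.771 | 23% | 0.91 / 0.89 | 0.80 |
| 0.6 | 0.822 | 18% | 0.81 / 0.80 | 0.74 |
| 0.7 | 0.874 | 13% | 0.70 / 0.69 | 0.66 |
| 0.9 | 0.976 | 2% | 0.41 / 0.40 | 0.40 |

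The ratio reaches 1 at ρ = 72/37 − 1 = 0.946.

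**Step 2: unequal SDs.** With follow-up SD equal to k times baseline SD, the ratio is k²(1−ρ²)(37/36) / (1+k²−2ρk).
- ρ 0.6, k 0.8: 0.421/0.680 = 0.619, a saving of 38%.
- ρ 0.6, k 1.25: 1.028/1.0625 = 0.967, a saving of 3%.
- ρ 0.7, k 1.25: 0.819/0.8125 = 1.008, no gain.

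With 18 or 16 per arm analysed (ρ 0.6, equal SDs), the saving is still 17-18%.

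**Step 3: against the interaction test that the plan states.** Effect 0.7 SD, every pair of visits correlated 0.6. The interaction is F(3,114). The adjusted joint test of arm and arm-by-visit over three post-baseline visits is F(3,35) with unstructured covariance.

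| Effect present at | Noncentrality, interaction | Power | Noncentrality, joint | Power |
|---|---|---|---|---|
| 1 week and 2 months | 12.25 | 0.83 | 13.62 | 0.85 |
| 1 week only | 9.19 | 0.70 | 9.36 | 0.68 |
| all three visits | 9.19 | 0.70 | 12.77 | 0.82 |

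Part of each difference is the covariance assumption. With about 109 residual df the joint test has power 0.87, 0.71 and 0.85.

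**Step 4: false positives for Aim 1 if either task suffices.** For independent tests: one measure per task, 1 − 0.95² = 0.0975; two measures per task, 1 − 0.95⁴ = 0.1855. Simulating the interaction test (20,000 null trials, visit correlation 0.6), as the between-measure correlation goes from 0 to 0.7, gives 0.093 to 0.082 with one measure per task and 0.188 to 0.137 with two. A repeat run gave 0.096 to 0.081 and 0.188 to 0.134. The ranges are therefore 8-10% and 13-19%. If correlations decay over time and no sphericity correction is made, they rise to 0.097-0.117 and 0.157-0.218.

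If both tasks were required, with one measure each, the chance when neither responds would be below 5% (0.05² = 0.25% if independent).

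**Step 5: adjustment together with Holm.** Holm's first step is at 2.5%. The detectable effect is then 0.82 SD adjusted against 0.80-0.81 for an uncontrolled change contrast at ρ 0.6, and 0.73 against 0.69-0.70 at ρ 0.7. Over both steps (40,000 simulated trials, ρ 0.6, effect 0.7 SD), per-task power is 0.71-0.72 against 0.67-0.69 if both tasks improve, and 0.66 against 0.67-0.69 if only one does. The familywise error is 0.042-0.050 against 0.083-0.099.

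**The case against.** **Baseline as a time level is inferred.** Data Analysis does not list the levels of time, and a GLM can carry covariates. This stands: the reading comes from taking that section together with Study Design. No other reading is stated, however, and no covariate is named.

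**The change contrast is valid.** A reader might infer that the planned analysis is biased. It is not: under sound random allocation the contrast is unbiased, and the issue is efficiency only.

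**The saving concerns a contrast that the plan does not name as its test.** This also stands. A reader might take the 13-33% as a gain over the planned interaction test. Step 3 shows that the joint adjusted test is roughly neutral against it unless the effect is already present at the immediate visit, which the protocol treats as exploratory.

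**The gain rests on assumed correlations and SDs.** Correct. Entry is restricted on baseline cognition, so a follow-up SD above the baseline SD is plausible for related task scores, and that is the case in which the gain fades.

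**Inflation is not demonstrated.** A reader might say that Aim 1 must exceed 5%, or quote 17-26% by counting three measures per task. The documents support neither. Hypothesis 1 does not say that one task is enough, and response may be only the raw record from which accuracy is scored. Nor do they say that every planned contrast is a separate test. What does stand is that the decision rule is missing.

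**Conclusion.** The point holds in a limited form and should be addressed. On precision, the plan as written appears to forgo a baseline adjustment that would make the 1-week comparison more efficient. The advantage is useful at low to moderate correlation, and small or absent at very high correlation or when the follow-up SD clearly exceeds the baseline SD. This is an improvement to a valid analysis, not the repair of an error. All sizes depend on assumed correlations and SDs.

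The missing primary measure and success rule is the firmer part, because no reading of the documents supplies them. The figures of 8-10% and 13-19% apply if success on either task counts and each test is run at 5%. They are not properties of a rule that the plan states.

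**What to change.** **Model.** For each outcome, analyse the post-baseline visits with arm, visit and arm-by-visit, and with that outcome's own baseline as a covariate. Add the score used to match the arms once the sponsor confirms which it is. The entry limit suggests the MATRICS composite, but BACS is also allowed.

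**Aim 1 test and rule.** Make the adjusted 1-week difference the main contrast. Before any arm-level result is seen, including for the early conference presentations, name one measure per task and state what counts as success. Holm across the two tasks at 5% is one suitable rule; requiring both tasks is another. Label other measures and visits secondary, the immediate visit exploratory, and unnamed contrasts descriptive. If a joint test is preferred, say whether it includes the immediate visit.

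**Cost.** Analysis wording only; no extra participants, visits or data. Fewer results can be called confirmatory. With Holm, net sensitivity is about unchanged at correlation 0.6, and the first step is somewhat less sensitive at 0.7, so the main return there is control of the false-positive chance.
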